Studies on performance measures: *Prospective studies:* The STORM-trial in Italy (8), the Oslo trial in Norway (7), and the Malmo-trial from Sweden (9) compared performance measures (i.e. recall rate, cancer detection, positive predictive value, tumor characteristics) within women screened with DM and DBT with DM or 2D. The STORM trial compared the outcome of sequential screen-readings; the same radiologists read DM first, and thereafter DBT. A significant higher rate of screen-detected cancer, 2.7/1000 and a lower recall rate was found for DM+DBT compared with DM. The Oslo trial assigned the radiologists to read DM or DM+DBT. They found an increase of 1.9 cancers/1000 screens using DM or 2D+DBT. The additional cancers were mostly invasive cancers. The recall rate decreased. The Malmo-trial compared the outcome of two-view DM with one view DBT. A significant increase of 2.6 cancers/1000 screened for one-view DBT was observed. The recall rate increased. The majority (17 of 21) of the cancers were invasive. *Retrospective studies:* Results from eight retrospective studies of DBT adjunct to DM are available of today (10-17). All the studies are conducted in the U.S. where the screening protocol differ substantially from the one used in Norway and Europe (18). Two of the studies (12, 13) compared performance measures before and after the introduction of DBT, while Haas et al. (10) compared the outcome of DM versus DM+DBT within the same timeframe. A clear trend toward a higher rate of screen-detected cancer and a reduction in recall rate were observed in all the studies.

Economic studies: Only two studies, both from the U.S. have considered the costs of DBT (27, 28). One of the studies concluded that DM+DBT resulted in cost savings compared with standard DM in a simulated screening cohort, mainly due to fewer recalls and earlier diagnosis, while the other study found that DM+DBT might be cost-effective for women with dense breasts.

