Gaps of knowledge related to DBT: Using DM+DBT seems to have the potential to decrease the recall rate, and to increase the positive predictive values of recalls (PPV-1) and needle biopsies (PPV-2), and the rate of screen-detected cancer, while the issue of interval cancer and cancer rate in the subsequent screening round is unknown. However, the results available of today is performed on equipment's from two vendors only, Hologic and Siemens. Equipment from the different vendors differ in constructions and the outcome is possibly different according to image quality, doses and outcome measures. No studies have reported results from screening women with DBT from GE, as far as we know. We expect 2D+DBT to have limited influence on recall rates in Norway since the rate is already as low as 2-3%, which is substantially lower than in the U.S. (18). Conversely, PPV-1 and 2 have potential for improvements. PPV-2 is not reported in studies using DM+DBT, so far. The effectiveness of mammographic screening is usually measured in terms of reduction in breast cancer mortality, rate of over-diagnosis, and interval cancer. To estimate these measures, 10 and 2-4 years of follow-up, respectively is needed (29, 30). It is not respectable to wait that long to state an effect, given the available data showing a higher detection rate by using DBT. The benefit of the increased detection rate is however controversial due to the issue of over-diagnosis. It is thus of substantial importance to figure out prognostic and predictive histopathological characteristics of the tumors detected with DBT versus DM.

An issue related to DBT is the increased radiation dose if DM is performed adjacent (26, 31). Using one view DBT may result in reduced dose compared with two view DM (32), while 2D+3D minimise the additional dose (32). Doses are shown to vary between vendors (33).

The economic aspects of implementing DBT is only reported from models based on data from the U.S. (27, 28). The results can hardly be transferred to Norway. Our project has the potential to explore all the parameters mentioned above.

Approaches, hypotheses and choice of methods: The Norwegian Breast Cancer Screening Program started as a pilot in four counties in 1996 and became nationwide in 2005 (18). Hordaland was one of the pilot counties. Further assessment take place at one of the 16 breast clinics in Norway. Haukeland University Hospital is the breast centre for Hordaland.

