How do the early performance measures given in study II+III differ by mammographic density? Volpara® is installed at the screening units at Danmarksplass and data is available for this study. We will use descriptive analyses to compare distributions and rates, while logistic regression analyses will be performed to estimate the odds ratio of recalls and breast cancer (37).

Studies V and VI: Costs of tomo and DM in a population based screening program – Is tomo cost-effective? Study V will deal with early costs related to time spent at screening and reading, the recall rates, diagnostic procedures, treatment and total costs for the two techniques. Data from the first year of the trial will be used. A previous study from Norway, which showed that treatment costs are highest during the first year following a diagnosis will serve as a methodological basis for the analysis (38). Using a similar approach, we will compare treatment costs for interval cancers, recurrence and early costs of cancers detected in the following screening round, using the full two year follow-up in Study VI. Results will be presented as cost per recurrence, interval and subsequent breast cancer avoided. Possible differences between groups in these outcomes should be well captured during the two years. Mortality may also be used as an additional outcome in the cost-effectiveness analysis in If the project is sufficient funded, study VI, although the follow-up time is too short, will use a simulation model with mortality estimates from the Cancer Registry. Additional cost estimates for the period beyond two years will be run (33) as inputs can be run to estimate the cost-effectiveness in the life-long perspective for the women (as e.g. in (28)). A major advantage of Studies V and VI compared with the U.S. studies (24, 25), is the availability of individual level data within the project, thus avoiding most assumptions of recall rates, cancer stage distributions, diagnostic and treatment costs etc. from earlier studies. This ensures a higher level of detail when defining the list of cost components, and more precise estimates of the variation across patients in both effect outcomes and costs.

A prospective cohort study: We will perform a prospective cohort study. During the study period, about 45,000 women will be invited to screening at Danmarksplass and 35,000 (75%) are expected to participate (Table 1).

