This project is aimed at performing a randomized trial investigating the effect of early performance measures and economic aspects of tomo versus DM in a screened population. All studies will be performed with data from women screened at Danmarkspllass. The pilot will be performed Aug-Dec 2015, while the trial period is set to Jan 2016-Dec 2017 (Table 2). Complete data for analyses of early performance measures related to the screening exam will be available after the end of the trial. However, we will follow the women for information about treatment and therapy, interval and breast cancer in the next screening round, recurrence and metastasis, two years after screening exam. These follow-up results are of utmost interest for the complete effect of tomo versus DM in a clinical and economic perspective.

Data collection: All studies will be based on the same dataset, except for # I and V, which are based on data collected from the first year of the trial.

Clinical data: Data related to screening participation will be extracted from the Norwegian Breast Cancer Screening Program's Database, located at the Cancer Registry of Norway. Technical data regarding mammographic density and radiation doses is considered part of the screening data. Data related to needle biopsies and treatment will be collected immediately after the diagnosis, particularly for this study, for the study period (2016-17) and the follow-up time (2018-19). These data is needed immediately to keep the study results updated and to keep the time schedule. A close collaboration with the pathologists and surgeons at Haukeland University Hospital ([name] and [name])

is already established. Research assistants will be responsible for collecting, reporting, and coding the trial and follow-up data.

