Sept 2015-Des 2018	Hiring research assistants – responsible for the practical part of the study, collecting, reporting and coding the histopathologic data
Jan 2016-Dec 2017	Running the trial
Jan 2017-Dec 2019	Hiring a PhD student
Jan-Dec 2017	Application for PhD + reviewing the literature Analysis and writing paper I – submission to a peer-reviewed journal
July-December 2017	Preparing programming code for cost data and analysis based on preliminary data
Jan 2018-Sept 2018	Analysis and writing paper II+V – submission to a peer-reviewed journal
Aug 2018-Dec 2018	Analysis and writing paper III – submission to a peer-reviewed journal
Oct 2018-Mar 2019	Analysis and writing paper IV – submission to a peer-reviewed journal
Oct 2018-Mar 2019	Evt Cost analysis – finalizing and submitting papers VI
Feb 2019-May 2019	PhD student: Working with the thesis – finalizing
May 2019-Dec 2019	Finalizing the papers, the project, and prepare for disputation
Dec 2019	Disputation
Jan 2020-Dec 2020	Finalizing the study: Analysing rates, histopathologic characteristics and mammographic features of interval and subsequent breast cancer – on own budget

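### Study VI counts next-round cancers avoided as a benefit without netting them against trial-screen cancers, and leaves treatment of trial-screen cancers undefined in the cost numerator

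*Combined protocol and SAP*

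**What the plan says.** The effect unit for Study VI is given in section 2 under Studies V and VI: "Results will be presented as cost per recurrence, interval and subsequent breast cancer avoided". The treatment costs for Study VI are described just before it: "we will compare treatment costs for interval cancers, recurrence and early costs of cancers detected in the following screening round". Cancers found at the trial screen appear in neither sentence.

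Treatment in general is placed in the companion paper: "Study V will deal with early costs related to time spent at screening and reading, the recall rates, diagnostic procedures, treatment and total costs". That paper has a restricted window: "Data from the first year of the trial will be used". Section 3 (Data collection) confirms the split: "All studies will be based on the same dataset, except for # I and V". Study VI therefore draws on the full data set. Section 3 (Data for cost analysis) adds that every diagnostic and treatment procedure during follow-up is recorded and given a cost.

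On extra detection, section 2 (Studies on performance measures) reports of the Oslo trial: "They found an increase of 1.9 cancers/1000 screens using DM or 2D+DBT". It also gives a 2.7 per 1000 higher rate for STORM. The section on gaps of knowledge adds: "The benefit of the increased detection rate is however controversial due to the issue of over-diagnosis". The last row of Table 2 plans a follow-up analysis in 2020: "Analysing rates, histopathologic characteristics and mammographic features of interval and subsequent breast cancer".

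**The concern.** Suppose tomo finds a cancer at the trial screen that DM would have found at the next screen. That cancer is then absent from the tomo arm's next round. The woman was still diagnosed and treated, only earlier. The Study VI effect unit would record her as a cancer avoided, and nothing in the text offsets this against the extra case at the trial screen. An over-diagnosed cancer behaves differently: it adds a case at the trial screen and removes none later, so it leaves no trace in the measure. The plan itself names over-diagnosis as the reason why the value of extra detection is disputed.

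No other planned analysis fills the gap. Study II covers screen-detected cancers in the trial period, and the 2020 analysis covers interval and next-round cancers. The sum of the three by arm is not described anywhere.

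The cost side has a matching gap. If the Study VI list were read as complete, treatment of trial-screen cancers from the second trial year would be named in neither economic study. At stake is a paper that could report cancers avoided, and perhaps money saved, when the tomo arm has as many cancers in total as the DM arm, or more. Longer follow-up would not correct this, because it arises from what is counted.

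**Working it through.** The documents state no Study VI figure, so there is no planned ratio to reproduce. The inputs can be checked against Table 1: 17,500 × 6.0/1000 = 105 screen-detected cancers and 17,500 × 2.0/1000 = 35 interval cancers per arm, as printed.

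**Inputs**
- n = 17,500 participants per arm (Table 1).
- x = 1.9 to 2.7 extra screen-detected cancers per 1000 (section 2, Studies on performance measures; the STORM figure is read as an increase over DM).
- f = share of the extra cancers that would otherwise have surfaced as interval or next-round cancers within follow-up. The documents give no value; 0.25 to 1 is assumed. The remainder, 1 − f, comprises over-diagnosed cancers and those that would surface after the window.
- r = cost of treating a later cancer relative to a trial-screen cancer. This is also assumed.
- The next-round examination is assumed to be the same in both arms, and tomo is assumed to prevent no cancer outright.

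**Cancer counts**

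Extra trial-screen cancers E = n × x: 17,500 × 1.9/1000 = 33.25, and 17,500 × 2.7/1000 = 47.25, so 33 to 47.

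Counted as avoided = f × E. Cumulative difference, tomo minus DM = E − f × E = (1 − f) × E.

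| f (assumed) | Counted as avoided | Cumulative tomo excess |
|---|---|---|
| 0.25 | 8–12 | 25–35 |
| 0.5 | 17–24 | 17–24 |
| 0.75 | 25–35 | 8–12 |
| 1 | 33–47 | 0 |

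Across this range the measure always shows cancers avoided, and the tomo arm never has fewer cancers in total.

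**Treatment costs** (c = cost of treating one trial-screen cancer; tomo minus DM; screening, reading and equipment costs left aside)

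- Trial-screen cancers left out: −f × r × E × c.
- Trial-screen cancers included: (1 − f × r) × E × c.
- The gap between the two is E × c, that is 33c to 47c, whatever f and r are.

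With f = 0.5 and r = 1, leaving them out gives −17c to −24c and including them gives +17c to +24c, so the sign changes. With f = 0.75 and r = 1.5, f × r = 1.125; leaving them out gives −37c to −53c and including them gives −4c to −6c, so the saving shrinks but remains.

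**The case against.** A reader might infer that the ratio favours tomo by construction on both sides. On costs the documents do not support that. The numerator of the ratio is never defined. The Study VI cost sentence says it follows a similar approach to Study V, which includes treatment and total costs, so it can be read as what Study VI adds. Study VI uses the full data set, and all procedures are collected and costed. Treatment of trial-screen cancers is therefore unnamed, not shown to be excluded. This part of the objection stands.

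A reader might also infer that many of the next-round cancers counted as avoided will only have been moved forward. The documents give no figure for that share. The 1.9 to 2.7 per 1000 come from other vendors' equipment and other reading designs; the plan warns that results may differ by vendor and knows of no screening results for the GE system. Table 1 plans the same number of cancers in each arm. This stands too: the counts above show direction, not a forecast.

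Two of the three effect units can be real benefits. Fewer interval cancers or recurrences may follow from earlier detection, and the plan does not say whether the three units are pooled or reported as separate ratios. If they are separate, the lead-time problem falls mainly on one.

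Finally, over-diagnosis is not ignored. Study II compares DCIS and invasive detection rates, Study III asks whether tomo-detected tumours are slow to progress, and a lifetime simulation is mentioned if funds allow. All components of a cumulative count are planned. What remains is that they are never added, and that the Study VI effect unit as worded does not draw on them.

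**Conclusion.** The point holds for the effect unit. As worded, Study VI treats a lower next-round count as benefit, with no rule separating a prevented cancer from one found a round earlier and no cumulative count beside it. On costs the finding is narrower: the numerator does not say whether treatment of trial-screen cancers from both trial years is included. It does not follow that those costs are left out, or that the ratio must favour tomo.

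The illustrative size is 33 to 47 extra trial-screen cancers, with 8–12 to 33–47 counted as avoided against a cumulative excess of 25–35 down to 0 as f goes from 0.25 to 1. This rests on detection gains carried over from other equipment, on an assumed f, and on equal next-round examinations. Should be fixed before Study VI is analysed. It does not touch randomisation, data collection or Studies I to IV.

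**What to change.** 1. Do not use next-round cancers avoided as a stand-alone benefit unit. Keep interval cancers and recurrence, each as a separate effect unit.
2. In Study VI, report cumulative cancers per 1000 randomised women by arm (trial screen plus interval plus next round), invasive and DCIS separately, with stage. Do the same in the 2020 follow-up analysis.
3. State that the cost numerator includes treatment of trial-screen cancers from both trial years, in both arms, over the same window.

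The cancers and the procedure codes are already to be collected, so the cost is wording and a little more analysis. The downside for the sponsor is that the result may look less favourable to tomo.

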We want to take advantage of the new mammographic equipment (Seno Claire GE Breast Tomosynthesis) installed at the screening unit at Danmarkspllass in Bergen, December 2014, and perform a randomized trial assessing 2D + DBT in two projections (hereafter referred as tomo) versus standard two projections DM as screening tools. The equipment is accepted for screening both in the US and Europe, but no results from studies on human beings are reported in articles of today (34, 35). Measuring the effect of tomo with GE versus standard DM can be done by comparing results of early performance measures and economic aspects in two comparable populations at the same age and residing in the same county, examined by the same radiographers, screen-read by the same radiologists and histologically breast cancer proven by the same pathologists, treated by the same surgeons and oncologists.

The project has a practical and an academic part: 1) The practical part is critical and consists of a four months pilot and 24 months (one screening round) of running the trial. The pilot is aimed at testing feasibility including the time aspect, get experiences and learn how to read tomo, develop a practical hanging protocol and a form to report information needed to assess the research questions right after the screening is performed and eventual diagnosis is stated. The trial will be run as a part of the screening program. Only small changes from the usual setting is acceptable. 2) The academic part aims at investigating early performance measures and economic aspects performed in the practical part. We aim to address the following topics and research questions in the academic part:

Study I: *Early performance measures in a population based screening program using tomo versus DM – interim analyses.* We will compare results of early performance measures.

How do the recall rates, including false positive screening results differ between the two groups? What time is spent in examination and reading with the two technologies? How do the radiation doses differ between the two groups? Due to the small number of women screened and diagnosed with breast cancer during the first year (Table 1), this study will focus on early performance measures related to the time used, recalls and radiation dose. We will compare the outcome for tomo versus DM and according to recommended levels given in the quality assurance manual (36) using standard statistical tests (37).

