
4. Key perspectives and compliance with strategic documents

Mammography is the preferable technology for breast cancer screening and diagnostic today. DBT is assumed to be the next generation screening technology for breast cancer (39). As of today, there is not sufficient evidence about the effect of tomo to implement the technology. This study has a unique possibility to contribute in filling the gap of knowledge needed to assess the technology's potential as a screening tool. If tomo turn out to be a better screening tool compared with DM, the benefits of participating in screening might be improved, whilst the harms will assumingly decline, which is beneficial both for the women screened negative and those diagnosed with breast cancer, both in Norway and in other countries.

Interim analyses will be performed after one year of performance of the study, while the final results will be available 3-6 months after the trial is finished. This is unique in a screening setting. In addition, we will follow the women for interval and subsequent cancer 2 years after the trial is finished. Results from the applied trial and the follow-up represent a unique possibility to analyse data from a substantial number of screened women which no other screening programs are able to do, due to the link between the clinical data, the screening database and data from the incidence database at the Cancer Registry. Norway is in a unique situation with the 11-digit PIN number, the

nationwide screening program and the Cancer Registry, which makes it possible to identify the cancer cases, even if women move from one county to another. These facts make this study unique from an international perspective.

The trial might be able to serve as an example for other screening and diagnostic tests, not only breast cancer and mammographic screening. Implementing new technology should be based on sufficient evidence. This protocol has the possibility to serve as a guide for testing screening and diagnostic tools for other diseases.

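### The plan gives two conflicting follow-up rules: the per-woman rule closes just as the next screening exam falls due, and Study VI is scheduled before either rule is complete

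*Combined protocol and SAP*

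**What the plan says.** The combined protocol and SAP describes follow-up in several places.

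- Section 3, opening paragraph: women are followed for treatment and for "interval and breast cancer in the next screening round, recurrence and metastasis, two years after screening exam". The same paragraph states that "the trial period is set to Jan 2016-Dec 2017".
- Section 4: "we will follow the women for interval and subsequent cancer 2 years after the trial is finished". With the trial ending in December 2017, this means December 2019.
- Section 3, Clinical data: biopsy and treatment data are collected "for the study period (2016-17) and the follow-up time (2018-19".
- Section 2, practical part: the trial consists of "24 months (one screening round) of running the trial", which sets one round at 24 months.
- Section 2, Studies V and VI: the analysis covers treatment costs for interval cancers and recurrence and "early costs of cancers detected in the following screening round, using the full two year follow-up in Study VI". It adds: "Possible differences between groups in these outcomes should be well captured during the two years". No calculation supports that sentence.
- Table 2: October 2018 to March 2019 is set aside for "Evt Cost analysis – finalizing and submitting papers VI". A separate 2020 row covers rates, histopathology and mammographic features of interval and subsequent cancers. It names no costs.

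**The concern.** The two rules are different designs. The first gives every woman 24 months. The second gives 24 to 48 months, depending on when she was screened. No passage says which one governs.

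The per-woman rule does not fit one of its own outcomes. A window equal to the length of a round closes when the next exam is due, so a cancer found at that exam falls either just inside or just outside it, with almost no time for treatment costs to accrue. Section 2 itself notes that treatment costs are highest in the first year after diagnosis.

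Study VI reports cost per recurrence, interval cancer and subsequent cancer avoided, and section 3 describes the follow-up results as very important to the full clinical and economic comparison. Those results depend on when the window closes and when the data are cut.

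**Working it through.** The documents give no figure for how many next-round cancers or costs fall inside the window, so there is none to reproduce. The one figure used here from Table 1 does reproduce: 17,500 × 6.0/1000 = 105 screen-detected cancers per arm.

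**Inputs from the documents.** Index exams from January 2016 to December 2017 (months 0 to 24); round of 24 months; per-woman window of 24 months; calendar end December 2019 (month 48); Study VI completed by the end of March 2019 (month 39).

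**Assumptions.** Entry is even over 24 months. The next round also yields 105 cancers per arm (full re-attendance, same rate). T is the number of months from the index exam to the next exam, with diagnosis at the exam. Costs accrue evenly over the first year after diagnosis.

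**Formulas.**
- Per-woman rule, share of next-round cancers lost: P(T > 24).
- Per-woman rule, share of first-year cost time seen: E[max(24 − T, 0)]/12.
- Calendar rule, share lost: E[max(T − 24, 0)]/24, because a woman with T > 24 is lost only if she entered in the last T − 24 months.

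**Results for T uniform over four illustrative spreads.**

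| T (months) | Per-woman: lost | Cancers per arm | First-year cost time seen | Calendar: lost | Cancers per arm |
|---|---|---|---|---|---|
| 22–25 | 1/3 = 33% | 35 | 0.667/12 = 5.6% | 0.167/24 = 0.7% | 0.7 |
| 22–26 | 2/4 = 50% | 52.5 | 0.5/12 = 4.2% | 0.5/24 = 2.1% | 2.2 |
| 23–26 | 2/3 = 67% | 70 | 0.167/12 = 1.4% | 0.667/24 = 2.8% | 2.9 |
| 22–28 | 4/6 = 67% | 70 | 0.333/12 = 2.8% | 1.333/24 = 5.6% | 5.8 |

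**Sensitivity.** A simulation with T normal, mean 24 and SD 2, gives 50% of next-round cancers captured and about 7% of first-year cost time under the per-woman rule. A one-month lag to diagnosis lowers these to 31% and 3%. Over means of 23 to 25 months, SDs from about 0 to 3 and lags of 0 or 1 month, cancers captured range from 0 to 100%, but first-year cost time only from 0 to 15%. Under the calendar rule the same scenarios capture about 90 to 100% of cancers and 66 to 79% of first-year cost time.

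**Unevenness under the calendar rule.** With T = 24, a woman entering at month e has 48 − e − 24 = 24 − e months after her next exam: about 24 for January 2016 and about none for December 2017. Half of the women have at least 12 months. The first-year cost time seen is 0.5 × 1 + 0.5 × 0.5 = 75%.

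**Study VI timing.** By the end of March 2019, women who entered by month 39 − 24 = 15 have 24 months: 15/24 = 62.5%. At the start of the slot (end of September 2018, month 33) the figure is 9/24 = 37.5%. With T = 24 and a March 2019 cut, 62.5% of next-round cancers are captured. Of their first-year cost time, (3 × 12 + 12 × 6)/(24 × 12) = 37.5% is seen.

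**Interval cancers.** These are much less affected. If they arise evenly over 24 months, even a March 2019 cut sees (15 × 24 + 9 × 19.5)/(24 × 24) = 93% of the interval time.

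**The case against.** The strongest reply is that the calendar rule is the intended one. Section 4 states it, the 2018-19 collection period fits it, and Table 2 leaves the analysis of interval and subsequent cancers to 2020. On that reading only about 1 to 6 next-round cancers per arm are lost. This stands. A reader might infer that the trial will lose half or more of its next-round cancers and nearly all their costs. The documents do not support that as a general statement: it holds only under the per-woman rule and, for the number of cancers, only under an assumed spread. The reply does not settle the matter, because section 3 states the per-woman rule outright, the 2018-19 period does not rule it out (24 months from the last exam also ends in December 2019), and the Study VI text speaks only of two years.

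Three other inferences go too far.

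- That these cancers are the plan's own test of over-diagnosis: section 2 answers that concern with tumour characteristics, in Study III.
- That interval and next-round cancers will be mixed: the plan names them separately, and exam dates in the screening database can separate them. What is missing is the written definition.
- That the comparison between arms is biased: the same window applies to both randomized arms. The loss is of events and costs.

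It is also fair to say that Study VI promises only early costs for next-round cancers, leaves later costs to a model if funded, and is marked as optional in Table 2. That limits the importance of the point. It does not rescue the statement that two years captures these outcomes well.

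**Conclusion.** The concern holds in a limited form. Three parts need no assumption about re-screening times: the two rules conflict, the per-woman window equals the round length, and Table 2 puts Study VI before follow-up is complete under either rule.

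The size depends on the rule. Under the per-woman rule, the share of next-round cancers missed is about half if exams centre on 24 months, and could be anything from none to all over the scenarios tried. The finding on costs is firmer, since at most 15% of first-year cost time is seen in any of them. Under the calendar rule most next-round cancers are captured, and the remaining problem is unequal follow-up after the next exam with no stated way of handling it. The counts per arm also assume full re-attendance and an unchanged detection rate.

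The power statement, Studies I to IV and the first-year cost study (Study V) do not depend on this point.

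**What to change.** 1. Adopt one definition per woman, based on events. Interval cancers are those diagnosed after the index screening episode and before the next exam, or within 24 months if she is not re-screened. Next-round cancers are those detected at the next attended exam, up to a stated cap.
2. State one registry data cut, late enough for women screened in late 2017 to complete their next exam, and analyse cancer outcomes in the existing 2020 slot.
3. For costs, either compare next-round cancers over an equal window after diagnosis, limited to women with that follow-up, or delete the claim that two years captures these costs. If the limit is set by index-exam date, the randomized comparison is kept. With data to December 2019, a 12-month window and T = 24, it leaves about 12/24 × 105 = 52 next-round cancers per arm.
4. Move Study VI after the data cut, and make section 2 (Studies V and VI), section 3, section 4 and Table 2 agree.

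**Cost.** For cancer outcomes the change is wording and a later extraction. The cap is constrained: 30 months from December 2017 is June 2020, and the registry lag of at least half a year given in section 3 (Data for cost analysis) brings this to about December 2020, the end of the slot. A cap of 27 months would reach about September 2020. A longer cost window is not clearly cheap. Treatment data come from project collection by research assistants, who are budgeted for 2015 to 2017 and listed in Table 2 only to December 2018, so a data source for later costs would have to be named. Study VI would be reported later.
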